2.3 ENDPOINTS

2.3.1 Primary Endpoint/Outcome

Physical Component Score (PCS) of the SF-36 HRQoL questionnaire at 90 days post-randomisation.

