4 STUDY POPULATION

4.1 NUMBER OF PARTICIPANTS

The total sample size is 346, allocated 1:1 between the two randomised groups.

We anticipate recruitment will take place in 20-25 sites UK-wide, but more sites will be included according to interest, resources, and recruitment rates. Sites outside the UK will be considered if feasible.

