7.2 Baseline

The following data will be collected:

Demographics: age, sex
Pre-existing health status:

- recalled SF-36 (PCS and MCS) 30 days prior to hospitalisation. Attempt to complete as close to the time of enrolment as possible. For patients lacking capacity at enrolment, this measure can be deferred until patients regain capacity
- Functional Co-morbidity Index (FCI)
- Clinical Frailty Index prior to the onset of the acute illness that resulted in this hospitalisation
- ICU Mobility Scale (IMS) at the time of randomisation
- Baseline health service utilisation questionnaire

Acute illness characteristics:

- ICU admission diagnosis
- APACHE II score
- o duration of mechanical ventilation
- o duration of renal replacement therapy (if required)
- SOFA score from the 24hrs period prior to the participant being ready for ICU discharge.

Blood sampling:

- 1. Blood required for cross matching: These samples should follow normal local procedures and are not considered research samples. Only send this sample if not available clinically and required for transfusion.
- 2. Hospital Laboratory (using local sampling volumes and processes): haemoglobin concentration; reticulocyte count; C Reactive Protein (CRP). These results should be collected for all trial participants. Existing results from samples taken <24hrs prior to randomisation can be used. It is acceptable to use the screening haemoglobin as the baseline haemoglobin if from <24 hours prior to randomisation. Use local procedures to 'add on' tests to appropriate existing clinical samples where possible (for example reticulocyte

count and CRP). If not available, the samples should be taken as part of clinical care but if not possible they should be taken as additional research samples.

Refer to section 5.1.3 for guidance on baseline Hb results and study procedures.

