9 STATISTICS AND DATA ANALYSIS

9.1 SAMPLE SIZE CALCULATION

Based on our previous research^{2 18} we estimated mean PCS SF-36 at 90 days will be significantly reduced at 35-40 (normal population average value 50), with standard deviation (SD) of 10-15 points. We defined a minimum clinically important difference as 5 points of the PCS element of the SF-36 at 90 days (smaller differences are of unlikely importance to patients)⁴¹. This represents an effect size of 0.42. Assuming the mean (SD) PCS will be 38 (SD 12) with restrictive (usual) care, to detect an improvement from RBC transfusion to a mean PCS of 43 at 90% power (two-sided P value 0.05) would require 244 patients.

In this population there is a risk of loss to follow-up (other than death), which in most previous trials has been between 10% and 30%. We originally proposed to inflate the sample size allowing for a 20% loss to follow-up at 90 days. This required a sample size of 305 (randomised 1:1 between the two groups). Adjusting for pre-specified baseline covariates is expected to further increase study power and/or protect against extra variability.

In May 2024, follow-up completion for the primary outcome was 75% despite active attempts to maximise this. As part of the strategy to ensure internal validity and adequate study power it was agreed to increase the sample size to ensure complete follow-up for at least 244 surviving patients. Rates of deaths during follow-up were

12/182 (7%). A conservative approach was agreed, assuming loss to follow-up might be as high as 30%. This required an inflation in sample size from 305 to 346 patients to ensure at least 90% power for a difference in the SF-36 PCS of 5 points.

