9.2 PROPOSED ANALYSES

All details of the statistical approaches will be specified in a comprehensive Statistical Analysis Plan (SAP), authored by the study statistician and approved by the independent oversight committees (TSC and DMC).

General considerations: will use the Intention-To-Treat (ITT) principle for all outcomes, to estimate treatment effectiveness. However, safety data will be analysed according to treatment actually received instead of treatment allocated.

Principle analysis of PCS SF-36 score: The primary endpoint (change from baseline PCS SF-36 score) at 90 days post randomisation will be compared between randomised groups using a mixed effects linear model, with site as a random effect, and adjustment for any strongly prognostic baseline parameters (which may include age, comorbidity score, pre-ICU recalled HRQoL, length of ICU stay, ICU mobility scale, and baseline inflammation (assessed by CRP concentration)). The expectation is that around 20-30% of those randomised will have some missing data on the primary endpoint. We will address these missing data using an appropriate model for the missing data-generating mechanisms and conduct sensitivity type analyses to investigate the robustness of the findings to the assumptions behind this model.

In addition to the full ITT approach for the primary endpoint, (i.e. the real-world effect of the intervention amongst all those offered the intervention) we will also estimate the treatment efficacy (the idealised effect achieved by those fully compliant with their randomised treatment and all aspects of the protocol).

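### Section 9.2 names the primary endpoint as change from a recalled pre-hospital PCS, while the rest of the protocol defines and powers it as the PCS at 90 days

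*Protocol*

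**What the plan says.** The endpoint section gives the primary outcome as "Physical Component Score (PCS) of the SF-36 HRQoL questionnaire at 90 days post-randomisation". The summary and the PICO question in 3.3.1 say the same. Section 5.2.3 on withdrawal also treats the day-90 PCS as the primary outcome, and section 6.2 puts the PCS first in the day-90 questionnaire order so that the primary outcome is secured.

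The sample size in 9.1 is on that scale: "We defined a minimum clinically important difference as 5 points of the PCS element of the SF-36 at 90 days", then "Assuming the mean (SD) PCS will be 38 (SD 12) with restrictive (usual) care" against a mean of 43, which "at 90% power (two-sided P value 0.05) would require 244 patients". With loss to follow-up allowed for, "The total sample size is 346, allocated 1:1 between the two randomised groups" (section 4.1).

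Section 9.2 differs. It describes "The primary endpoint (change from baseline PCS SF-36 score) at 90 days post randomisation", compared between groups in a mixed model with site as a random effect and "adjustment for any strongly prognostic baseline parameters (which may include age, comorbidity score, pre-ICU recalled HRQoL" and others.

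The only baseline PCS listed in 7.2 is a recalled score referring to 30 days before hospitalisation. On its timing: "For patients lacking capacity at enrolment, this measure can be deferred until patients regain capacity". Section 10.4 states that the trial is not blinded.

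**The concern.** A level at 90 days and a change from baseline are different primary variables. They can differ in variance, in which patients have an observed value, and in the p-value. The protocol defers statistical detail to a separate analysis plan, but this is not a detail that it leaves open. It names two endpoints, so any analysis plan must depart from one of the two statements.

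The choice of baseline makes the change score harder to defend here:

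- **Reference state.** The change is measured from pre-illness health, not from the patient's state at randomisation.
- **Timing.** When capacity is lacking at enrolment, the recall is given after allocation, by a patient who may know the allocation. Inside a change score, any difference between arms in how patients recall goes straight into the treatment effect.
- **Missingness.** Without a recall the change score is undefined, even when the 90-day PCS has been obtained.
- **Power.** The 244 was derived from the SD of the 90-day score. It does not carry over to an unadjusted change score unless the recalled and 90-day scores are sufficiently correlated.

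**Working it through.** **Inputs from section 9.1:** difference 5 points, SD 12 at 90 days, two-sided 0.05, 90% power, 244 evaluable. **Not in the protocol, so assumed:** the SD of recalled PCS (12, then 10 and 15) and its correlation r with the 90-day PCS (0.3 to 0.7).

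**1. The plan's own figure.** n per arm = 2 × (1.960 + 1.282)² × 12² / 5² = 121.05, rounded up to 122, so 244. A two-sample t-test with 122 per arm has 90.0% power. Then 244 / 0.80 = 305, and 346 × 0.70 = 242, close to 244. The sample size is therefore reproduced on the 90-day score.

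**2. Power with the same 244.** Randomisation balances the pre-hospital score in expectation, so the target difference stays 5 points. Only the SD changes:

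- unadjusted change score: SD = 12 × √(2(1 − r))
- 90-day score adjusted for recalled PCS: SD = 12 × √(1 − r²)

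| r | SD of change | Power, change | Adjusted SD | Power, adjusted 90-day PCS |
|---|---|---|---|---|
| 0.3 | 14.20 | 78.2% | 11.45 | 92.5% |
| 0.4 | 13.15 | 84.1% | 11.00 | 94.3% |
| 0.5 | 12.00 | 90.0% | 10.39 | 96.3% |
| 0.6 | 10.73 | 95.2% | 9.60 | 98.2% |
| 0.7 | 9.30 | 98.7% | 8.57 | 99.5% |

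The power figures are from a two-sample t-test with 122 per arm and ignore the site effect.

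**3. Break-even.** The variance of change is 12² + s² − 2r × 12 × s, where s is the baseline SD. This exceeds 12² when r < s / 24. Break-even is r = 0.42 for s = 10, 0.50 for s = 12 and 0.63 for s = 15.

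**4. With recalled PCS as a linear covariate.** Write Y for the 90-day score, B for the recall and T for treatment. The model Y − B = a + τT + bB is the same as Y = a + τT + (b + 1)B. The effect τ, the residuals and the standard error are unchanged. A check on simulated data gave 7.759 (SE 1.320) both ways.

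**5. Differential recall.** In an unadjusted change score the bias is the share deferred × the difference between arms in recall error. As an illustration only, 15% × 5 points = 0.75 points. With the recall as a covariate, the error is multiplied by the regression slope, which is about r when the SDs are equal. At r = 0.3 that is about 0.3 × 0.75 = 0.23 points, which is smaller but not zero.

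**6. Secondary outcomes.** Section 9.2 analyses continuous secondary outcomes in the same way as the primary. Section 7.2 lists no baseline fatigue or disability questionnaire, so the change reading cannot be computed for those outcomes. The level reading can.

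**The case against.** The best defence is that the conflict may have little numerical effect. Section 9.2 lists recalled HRQoL among the candidate covariates, 9.1 expects gains from pre-specified covariates, and section 1.3 criticises earlier trials for not adjusting for baseline health. An adjusted model is therefore the likely plan, and under it the two outcomes coincide. The final covariate list is normally settled in the analysis plan. This stands, and it makes the power loss conditional. It does not remove the contradiction, because the covariate is optional as written and an unadjusted change score is permitted.

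A reader might infer more than the protocol supports in three ways:

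- **That the trial is underpowered.** This needs both the omission of recalled PCS as a covariate and a correlation below break-even. Above it, the change score exceeds the planned 90%.
- **That patients without a recall are dropped.** Section 9.2 plans a missing-data model and sensitivity analyses, and nothing specifies a complete-case analysis. What follows is narrower: an outcome that could have been observed has to be imputed or excluded.
- **That deferred recall will be common.** The figure of about 15% in 5.2 is delirium at ICU discharge. Enrolment may come up to seven days after the patient is judged ready for discharge, and patients are to be approached with capacity where possible. Section 5.2.2.3 describes failure to regain capacity or to obtain consent to continue as rare. The deferral rate is not given, and bias would also require recall to differ by arm.

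**Conclusion.** The contradiction stands in current text and should be resolved before analysis. One section defines the primary endpoint as a change, while the summary and at least four other sections define, power or prioritise it as the 90-day level. That conclusion needs no assumption.

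The consequences are conditional. Without recalled PCS as a covariate and with a baseline SD of 12, power with 244 patients runs from 78% at a correlation of 0.3 to 99% at 0.7, against a stated 90%. The loss disappears if recalled PCS is a linear covariate. The adjusted 90-day score is at least as powerful as either alternative across the range examined, so nothing is given up by choosing it. The effects of missing and deferred recalls are real in direction but cannot be sized from the protocol, and they are secondary.

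**What to change.** In section 9.2, remove the parenthesis that defines the endpoint as a change, so that the sentence names the SF-36 PCS score at 90 days, as in 2.3.1 and 9.1. In the same paragraph, make recalled PCS a fixed, pre-specified covariate in the mixed model rather than an optional one. State that patients with an observed 90-day PCS and no recall stay in the analysis, with only the covariate imputed.

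As a secondary step, if the date of the recall is recorded, add a sensitivity analysis that treats recalls taken after randomisation as missing. The protocol does not say whether that date is captured, so this should be checked first.

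The cost is one or two sentences in the protocol and matching text in the analysis plan. The main change needs no new data and leaves the sample size as it is.

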- 6. Consent provided (by participant or in accordance with appropriate mental capacity legislation for the site)

Exclusion criteria

- 1. Contraindication or objection to RBC transfusion
- 2. Active bleeding when screened
- 3. Primary neurological ICU admission diagnosis, including primary brain or spinal cord injury
- 4. Patients discharged from the ICU following cardiac surgery
- 5. Currently receiving or planned to receive end-of-life care
- 6. Not expected by clinical team to survive to hospital discharge.
- 7. Patient with a proven chronic haematological disease that requires regular RBC transfusion to treat anaemia
- 8. Patient with dialysis-dependent chronic renal failure prior to ICU admission
- 9. Patient receiving regular erthyropoietin (or any erythropoiesis stimulating agent) treatment for anaemia prior to ICU admission.
- 10. Unable to obtain consent (from patient or in accordance with appropriate mental capacity legislation for the site)
- 11. Readmission to ICU during current hospitalisation episode and not enrolled following previous ICU admissions
- 12. Patient recovering following liver transplantation, kidney transplantation, or combined kidney/pancreas transplantation
- 13. Patient recovering from variceal bleeding due to chronic liver disease
- 14. Prisoners
- 15. Patient due for imminent hospital discharge within the next 24 hours

RANDOMISATION: Allocation 1:1 by remote computer randomisation (stratified by centre in blocks).

TREATMENT GROUPS:

Intervention group: All patients will receive a single unit RBC transfusion post-randomisation. Single RBC transfusions will subsequently be administered to achieve and maintain Hb 100-120g/L until hospital discharge. Hb measured at least weekly in hospital. Hb transfusion trigger <100g/L

Comparator 'usual care' group: Current usual care transfusion practice, namely single RBC transfusions when Hb less than 70g/L (or modified according to clinician decision) to achieve target Hb 70-90g/L. Hb measured at least weekly in hospital.

Co-interventions: all other aspects of care will be according to clinician decisions. Other treatments for anaemia, such as iron therapy, will be permitted in both groups but decided by treating clinicians.

Duration of intervention: From randomisation until acute hospital discharge (typically 2-3 weeks).

OUTCOMES:

Primary outcome: Physical Component Score (PCS) of the SF-36 HRQoL questionnaire at 90 days post-randomisation.

Secondary outcomes:

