3.1.1 Personalised Medicine

We recognise the need for *personalised medicine*, especially in relation to the use of blood transfusions, and will use novel approaches to explore two key issues that will inform which patients may gain greatest benefit from this intervention:

Prediction (moderation) variables (what baseline covariates influence treatment success): the importance of baseline co-morbidity, HRQoL, mobility and/or baseline severity of systemic inflammation (based on C Reactive Protein) will be studied within the trial, and a prediction model developed to help identify who will or will not benefit from blood transfusions.

Mediation variables (what variables measured early after randomisation are on the causal pathway for clinical benefit):

the importance of *systemic inflammation* and *impaired erythrogenesis* post-ICU will be studied within the trial to improve our understanding of the causal pathway whereby transfusions may improve recovery.

These variables may be useful to identify if treatments were working, as surrogate outcomes, or to assist clinical decision-making.

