6.1.2 Assessment and management during intervention period

The local care and research teams, in accordance with the protocol, will carry out the management of the patient during the intervention period.

6.1.2.1 Measurement of haemoglobin concentration:

Measurement of haemoglobin concentration in the acute hospital will be at the discretion of the clinical teams unless haemoglobin concentration is not measured as part of routine care for seven consecutive days.

If seven days have passed since the previous haemoglobin concentration measurement, the research team will request that the clinical team undertakes a measurement. This will only apply during the intervention period.

6.1.2.2 Transfusion practice during the intervention for patients randomised to the usual care transfusion practice

Patients should be managed according to current NICE guidance (see: www.nice.org.uk/guidance/ng24/chapter/Recommendations#red-blood-cells-2)

For the purpose of the trial this means:

Use restrictive red blood cell transfusion thresholds for patients who need red blood cell transfusions and who do not have major haemorrhage or have acute coronary syndrome.

Use a threshold of less than 70 g/litre and a haemoglobin concentration target of 70–90 g/litre after transfusion, unless the responsible clinician decides to modify this based on the patients' condition.

Use single-unit red blood cell transfusions for adults who do not have active bleeding and recheck Hb within 24-48 hours of the transfusion

This guidance should be followed after each haemoglobin concentration measurement undertaken during the intervention period (minimum one measurement per seven days).

6.1.2.3 Transfusion practice during the intervention for patients randomised to the intervention (more liberal) transfusion practice

Patients should be managed as follows following each haemoglobin concentration measurement undertaken during the intervention period:

If the haemoglobin concentration is ≥100g/L no transfusion should be given.

If the haemoglobin concentration is <100g/L a single-unit red blood cell transfusion should be given followed by clinical reassessment and re-checking the haemoglobin concentration.

If the haemoglobin concentration remains <100g/L further single unit red blood cell transfusions should be given until the haemoglobin concentration is 100-120g/L.

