Moderation analyses of PCS SF-36 Score: We will conduct pre-specified moderation analyses on the primary endpoint. These moderation analyses will fit interaction terms for the baseline parameters and treatment group. There are 4 baseline potential moderators of interest – (a) Co-morbidity score (0-18; functional comorbidity index; a count of morbidities); (b) Recalled SF-36 score pre ICU admission; (c) ICU mobility scale (ordinal scale); and (d) Baseline level of systemic inflammation (CRP concentration; continuous measure ranging upwards from zero with normal values being <5mg/L). These analyses will explore how important these baseline parameters are in moderating how effective the intervention is for the main outcomes. We will first explore the nature of the potential interaction by fitting each baseline parameter as a continuous interaction with treatment, and if warranted, look at suitable categorisation (e.g. above vs. below the median) for ease of clinical interpretation.

Mediation analysis of PCS SF-36 score: We are also interested in understanding the mechanisms behind any treatment effect. To this end, in the main trial analysis we will conduct mediation analyses on the model described under "Principal analysis of PCS SF-36 score." The first mediation analysis will examine the role of haemoglobin concentration (anaemia severity) using blood measurements taken at baseline and 30 days post-randomisation, to determine whether this mediates the intervention's effect. Specifically, we want to assess whether the degree of anaemia correction at

30 days, according to group allocation, relates to the endpoint. The second mediation analysis will focus on systemic inflammation. Here, we will explore whether persistent inflammation mediates the impact of the number of blood transfusions on the endpoint. We will consider other potential mediators, and include these in the final SAP prior to locking the trial database.

We also plan to measure a range of biomarkers that may provide information about the mechanisms that the intervention influences the primary outcome, based on blood sampling at baseline and 30 days. These will include effects of the intervention on iron status, marrow erythrogenesis (red blood cell production), inflammation, and immune suppression. These exploratory analyses will be underpinned by a Directed Acyclic Graph (DAG) and pre-specified analysis plan.

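### The inflammation mediation analysis takes the number of transfusions, a non-randomised count, as its exposure, so confounding by severity of illness can bias it

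*Protocol*

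**What the plan says.** Section 9.2 of the protocol gives the purpose of the mediation work: "We are also interested in understanding the mechanisms behind any treatment effect". It adds that "in the main trial analysis we will conduct mediation analyses on the model described under" the principal analysis, and that analysis compares the randomised groups.

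Two mediation analyses are then named.

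- **Haemoglobin.** The question is whether the degree of anaemia correction at "30 days, according to group allocation, relates to the endpoint".
- **Inflammation.** Here "we will explore whether persistent inflammation mediates the impact of the number of blood transfusions on the endpoint".

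The exposure thus changes from allocation to a count of transfusions. The section does not say whether allocation stays in the second model, or which units are counted.

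Other sections show what determines the count.

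- **Intervention group.** The summary states that "All patients will receive a single unit RBC transfusion post-randomisation". Under section 6.1.2.3, if haemoglobin stays low, "further single unit red blood cell transfusions should be given until the haemoglobin concentration is 100-120g/L".
- **Usual care group.** Section 6.1.2.2 gives a haemoglobin threshold and target, "unless the responsible clinician decides to modify this based on the patients' condition".
- **Time at risk.** Section 6.1.1 runs the intervention until discharge from the acute hospital.
- **Suspension.** Section 5.2.3 lets clinicians suspend allocation, for example for bleeding, acute cardiovascular events or deterioration.

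**The concern.** A mediation analysis that is meant to explain a randomised effect gets its protection from the randomised exposure. The effect of allocation on the mediator and its total effect on the outcome are both unconfounded. Once the exposure is the number of units, that protection is lost. The paths from exposure to mediator, from exposure to outcome and from mediator to outcome all become observational.

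The protocol itself makes a common cause plausible. Section 1.1.2 reports that persisting anaemia goes with low quality of life and is worst in patients with early persisting inflammation. A patient who recovers slowly has more days in which to be transfused, more reason for low haemoglobin, more inflammation at 30 days and a lower Physical Component Score (PCS) at 90 days.

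At stake is the mechanistic conclusion. The analysis could report that transfusion impairs recovery through inflammation when transfusion affects neither. It could also hide a real mechanism.

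**Working it through.** **1. The plan's own figures.** The protocol gives no figure for the mediation analyses, so the only one to reproduce is the sample size. With a difference of 5, SD 12, two-sided 0.05 and 90% power (section 9.1):

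n per group = 2 × (1.960 + 1.282)² × 12² / 5² = 121.1, rounded up to 122, or 244 in total. This agrees with section 9.1. With 346 randomised and 30% lost, 346 × 0.70 = 242 remain, and 242 is used below.

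**2. Null simulation with the count as exposure.** There were 2,000 trials per setting. Neither allocation nor units affected inflammation or PCS. Everything in this list except the 242 patients and the mean of 38 is an assumption, not a figure from the protocol.

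- Severity S is standard normal and unmeasured. A measured baseline marker B has correlation r with S and is adjusted for.
- Units are Poisson with mean 0.4 (usual care) or 1.5 (intervention) × exp(kS − k²/2), plus one unit for everyone in the intervention group. The group means are 0.4 and 2.5.
- Inflammation = 0.5 S + noise, total SD 1.
- PCS = 38 − 3.6 S − 3.0 × inflammation + noise (SD 9). The total SD is about 10.7, against the planned 12.
- Total effect: slope of PCS on units, given B. Indirect effect: slope of inflammation on units × slope of PCS on inflammation given units and B. False positive: the total-effect slope significant at two-sided 5%.

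| r | k | Units only: total / indirect (PCS points per unit) | False positive | Units with allocation in model: total / indirect | False positive |
|---|---|---|---|---|---|
| 0 | 0.3 | −0.68 / −0.31 | 30% | −1.37 / −0.64 | 53% |
| 0 | 0.6 | −1.12 / −0.51 | 75% | −1.98 / −0.87 | 94% |
| 0.5 | 0.3 | −0.51 / −0.22 | 20% | −1.02 / −0.43 | 35% |
| 0.5 | 0.6 | −0.88 / −0.37 | 55% | −1.59 / −0.66 | 81% |
| 0.8 | 0.3 | −0.24 / −0.09 | 8% | −0.50 / −0.18 | 12% |
| 0.8 | 0.6 | −0.45 / −0.16 | 19% | −0.84 / −0.30 | 31% |
| 0.95 | 0.3 | −0.08 / −0.02 | 6% | −0.15 / −0.05 | 6% |
| 0.95 | 0.6 | −0.12 / −0.04 | 6% | −0.22 / −0.08 | 7% |
| 0.5 | −0.3 | +0.53 / +0.22 | 22% | +1.07 / +0.44 | 38% |

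With k = 0 (severity does not drive the count) there was no bias, and false positives were 4% to 6%. In the last row sicker patients get fewer units, and the sign reverses. Adding allocation roughly doubled the bias in most rows, because only within-group, non-randomised variation in units is then left to estimate the slope.

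**3. Allocation as exposure, same data.** The mean total effect was −0.07 to +0.05 points, the mean indirect effect was within 0.03 of zero, and false positives were 4% to 6% in every setting.

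**4. What allocation does not protect.** In step 3 allocation has no effect on inflammation, which is favourable to the fix. A second simulation (2,000 trials per setting, 242 patients, PCS SD 12, severity slope on PCS of −3, −4 or −6, correlation of severity with inflammation 0.5) let allocation raise inflammation by 0.3 to 0.5 SD and gave inflammation no effect on PCS. Mediation was declared when both paths had p < 0.05. False mediation occurred in 32% to 95% of trials unadjusted, 8% to 39% with a marker of r = 0.8, and 4% to 8% with r = 0.95. The path from inflammation to PCS therefore needs adjustment whichever exposure is used.

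**The case against.** The strongest defence is that the protocol states a question, not an estimator. Section 9.2 leaves the details to the statistical analysis plan, bases mediation on a model that contains allocation, lists baseline covariates including CRP, and promises a causal diagram. The analysis is also exploratory, and no decision depends on it.

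Parts of this stand. An instrumental-variable analysis would fit the quoted sentence, so naive regression on the count is an inference. The primary result is untouched.

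The rest does not answer the point.

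- Keeping allocation in the model leaves the bias in place (step 2).
- The covariates are optional and all measured at or before baseline. They cannot capture later bleeding, deterioration or length of stay.
- The causal diagram is promised in the following paragraph, for the exploratory biomarker analyses. Whether it covers this analysis is at best arguable.
- The exposure is named in the protocol, not left open.

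A reader might go further and infer that severity is bound to show up as a harmful transfusion effect. The documents do not support that. Suspension of allocation, early death or transfer could reduce units in sicker patients and reverse the sign, and good baseline covariates could remove most of the bias. Nor can the simulated rates be read as the plan's error rates, because their inputs are assumed. Section 3.1.1, which describes the aim as "to improve our understanding of the causal pathway whereby transfusions may improve recovery", is a general statement and not a second instance of the problem.

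**Conclusion.** The point holds as a defect in the choice of exposure. As worded, the second mediation analysis asks about a post-randomisation count, although the stated aim concerns the effect of the randomised strategy and the companion analysis follows allocation. Confounding by severity can bias both the total and the indirect effect.

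Apparent harm is the most plausible direction, because low haemoglobin and a longer stay both add units. This rests on the assumption that sicker patients receive more units on balance.

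The size cannot be known from the protocol. It depends on how strongly severity drives the count and how much of severity the baseline covariates capture. Under the assumed inputs the result runs from negligible to a bias of about 1 PCS point per unit without allocation in the model, and about 2 points with it. For comparison, the protocol's minimum important difference between groups is 5 points.

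This should be changed, but it does not threaten the trial's main conclusion.

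**What to change.** Replace the sentence in section 9.2 with wording such as: *The second mediation analysis will examine whether inflammation at 30 days mediates the effect of allocated group on PCS at 90 days. The path from mediator to outcome will be adjusted for baseline CRP and the prognostic covariates. This path is observational and remains open to residual confounding.*

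If a per-unit analysis is kept:

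- Label it observational and exploratory.
- Count only units given before the 30-day sample. Section 2.3.2 records red cell use over 90 days, so an unrestricted count could include units given after the mediator was measured.
- Use allocation as an instrument for units and state the assumptions. The main one is that allocation affects PCS only through units, which needs defending in an unblinded trial (section 10.4) with a self-reported outcome. A single instrument gives the total per-unit effect. It does not by itself split that effect into direct and indirect parts.
- Otherwise present units descriptively by group.

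The cost is a few sentences in the protocol, matching text in the analysis plan and the corresponding code. No extra data, patients or change to care are needed.
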